10.3.3.8. Health Outcome/Quality of Life Analyses47
10.3.4. Interim Analyses47
11. References49

List of Tables

Table		Page
Table JTJH.2.1.	Schedule of Screening Activities	10
Table JTJH.2.2.	On-Study-Treatment Schedule of Activities.....	12
Table JTJH.2.3.	Post-Treatment Follow-Up Schedule of Activities	14
Table JTJH.2.4.	Continued Access Schedule of Activities.....	15
Table JTJH.4.1.	Objectives and Endpoints	21
Table JTJH.7.1.	LY2606368 for Injection Strengths.....	27
Table JTJH.7.2.	Hematologic Parameters Required for the Start of Each Cycle.....	28
Table JTJH.7.3.	LY2606368 Dose Reductions	29

List of Figures

Figure

Page

Figure JTJH.7.1. Continued access diagram.....31

List of Appendices

Appendix		Page
Appendix 1.	Abbreviations and Definitions	52
Appendix 2.	Study Governance, Regulatory, and Ethical Considerations	55
Appendix 3.	Clinical Laboratory Tests.....	58
Appendix 4.	Sampling Schedule for Pharmacokinetics	59
Appendix 5.	Hepatic Monitoring Tests for Treatment-Emergent Abnormality	60
Appendix 6.	Creatinine Clearance Formula.....	61
Appendix 7.	Protocol Amendment I4D-MC-JTJH(a) Summary A Phase 2 Study of LY2606368 in Patients with Extensive Stage Disease Small Cell Lung Cancer.....	62

1. Synopsis

Protocol Title: A Phase 2 Study of LY2606368 in Patients with Extensive Stage Disease Small Cell Lung Cancer

Rationale:

Small-cell lung cancer patients with extensive stage disease (ED-SCLC) are commonly treated with cisplatin or carboplatin in combination with etoposide. While a majority of patients respond to initial treatment, nearly all patients relapse and die from their disease. Consequently, new agents are needed to improve clinical outcomes for ED-SCLC patients. Study I4D-MC-JTJH (Study JTJH) will evaluate the efficacy of LY2606368 in both platinum-sensitive and platinum-resistant/refractory patients.

Objectives and Endpoints:

Objectives	Endpoints
Primary	

 Cohort 1: To estimate the ORR when a dose of 105 mg/m² LY2606368 every 14 days is administered to patients with ED-SCLC that have platinum-sensitive disease Cohort 2: To estimate the ORR when a dose of 105 mg/m² LY2606368 every 14 days is administered to in patients with ED-SCLC that have platinum resistant/refractory disease 	
 Best overall response (PR+CR) as determined per RECIST version 1.1
Secondary	

 To characterize the safety and toxicity profile of LY2606368 	
 The safety endpoints evaluated will include but are not limited to the following: AEs, SAEs, clinical laboratory tests, ECGs vital signs, and physical examinations

 To characterize the PK of LY2606368 	
 LY2606368 concentration in plasma

 To estimate secondary efficacy measures including DCR, DoR, PFS, and OS 	
 DCR: best overall response (CR, PR) and SD as determined per RECIST, version 1.1 DoR: time from the date of an objective response until PD, per RECIST 1.1 or the date of death from any cause in the absence of PD PFS: time from enrollment until the first radiographic documentation of progression or death from any cause in the absence of PD OS: time from enrollment until death from any cause

 To evaluate the association between best tumor response and change from baseline in lung cancer-specific symptoms, symptomatic distress, activity status, overall quality of life, total LCSS score, and ASBI for patients who have platinum-sensitive or platinum-resistant/refractory SCLC 	
 Lung cancer symptoms (appetite loss, fatigue, cough, dyspnea, hemoptysis, and pain), summation items (symptomatic distress, activity level, and global quality of life), total LCSS, and ASBI

Abbreviations: AEs = adverse events; ASBI = Average Symptom Burden Index; CR = complete response; DCR = disease control rate; DoR = duration of response; ECG = electrocardiogram; ED-SCLC = extensive-stage disease small cell lung cancer; LCSS = Lung Cancer Symptom Scale; ORR = overall response rate; OS = overall survival; PD = progressive disease; PFS = progression-free survival; PK = pharmacokinetics; PR = partial response; RECIST = Response Evaluation Criteria In Solid Tumors; SAEs = severe adverse events; SD = stable disease.

Overall Design:

Study I4D-MC-JTJH (JTJH) is a multicenter, Phase 2 study of LY2606368 in patients with ED-SCLC who have either platinum-sensitive or platinum-resistant/refractory disease. Cohort 1 will include patients with objective response to prior platinum-based therapy with subsequent progression ≥ 90 days after the last dose of platinum. Cohort 2 will include patients that either did not have an objective response to prior platinum-based therapy or had progression < 90 days after the last dose of platinum. Patients cannot have received more than 2 prior therapies for ED-SCLC.

Number of Patients:

Approximately 134 patients will be entered into Study JTJH, and 116 patients will be enrolled and complete the trial.

Treatment Arms and Duration:

Dose and Schedule (q 14 Days)		
Cohort	LY2606368 D1	Number of Cycles
1 and 2	105 mg/m ²	Treatment will continue until a discontinuation criterion is met.

Abbreviations: D = day; q = every.

2. Schedule of Activities

Table JTJH.2.1. Schedule of Screening Activities

Study Period		Baseline			
Cycle		BL			
Visit		0			
Duration		Up to 28 days			
Relative Day		≤28	≤14	≤7	
Procedure Category	Procedure				Comments
Study Entry/Enrollment	Informed Consent Form signed (prior to conducting any protocol specific tests/procedures)		X		
	Inclusion/Exclusion evaluation		X		
Medical History	Initial history/preexisting conditions		X		
	Historical illness		X		
	Habits assessment		X		Includes smoking history.
Physical Examination	Physical examination		X		Includes height and weight.
	ECOG performance status		X		
	Vital signs		X		
Tumor Assessment	Radiologic imaging according to RECIST 1.1		X		Baseline radiological tumor assessment per RECIST version 1.1 should be done (see Section 9.1). Radiologic assessments obtained previously as part of routine clinical care may be used as the baseline assessment provided that they were done no more than 28 days before the first dose of study drug.
	Tumor measurement (palpable or visible)		X		Performed at the same time as radiologic imaging.
Adverse Events Collection/CTCAE Grading			X		
Concomitant Medication Notation			X		
Laboratory/Diagnostic Tests	Hematology		X		
	Chemistry		X		
	Urinalysis		X		
	Coagulation		X		
	Pregnancy test	X			Women of childbearing potential must have negative serum pregnancy tests at their baseline visits and have negative urine pregnancy tests within 7 days before their first doses of LY2606368 (see Section 6.1).
	ECG		X		Single local ECG
	Confirm availability of pretreatment tumor tissue		X		If archived tissue is not available, a fresh tumor biopsy should be obtained after all other study entry criteria have been confirmed, unless the sponsor and investigator document that the patient may be enrolled without pre-treatment tissue.
	Exploratory blood sample for biomarkers			X	
	Optional pretreatment biopsy		X		Optional and may be performed at any time before starting treatment with LY2606368. See Section 9.8.2.
Health Outcome Measure	Lung Cancer Symptom Scale		X		The LCSS should be administered prior to extensive interaction with site personnel.

Schedule of Screening Activities

Abbreviations: BL = baseline; CTCAE = Common Terminology Criteria for Adverse Events (NCI 2009);
ECG = electrocardiogram; ECOG = Eastern Cooperative Oncology Group (Oken et al. 1982); LCSS = Lung
Cancer Symptom Scale; RECIST 1.1 = Response Evaluation Criteria In Solid Tumors Version 1.1 (Eisenhauer
et al. 2009).

Table JTJH.2.2. On-Study-Treatment Schedule of Activities

Study Period		Study Treatment Period						Comments
		1		2		3-n ^a		
Cycle/Visit		14 days		14 days		14 days		
Duration		14 days		14 days		14 days		
Relative Day within Dosing Cycle		1	8	1	8	1	8	
Procedure Category	Procedure							
Physical Examination	Physical Exam	X		X		X		Includes weight and calculated BSA. May be completed up to 7 days prior to treatment infusion. In Cycle 4 and beyond may be completed every other cycle (for example, Cycle 4, 6, 8, etc.).
	Vital signs	X		X		X		Includes blood pressure, pulse, and temperature. Complete before treatment infusion.
	ECOG performance status	X		X		X		Complete before treatment infusion.
Laboratory/ Diagnostic Tests	Hematology	X	X	X	X	X	X	May be drawn up to 3 days before the planned assessment. In Cycles 4-n, the Day-8 sample may be collected at the discretion of the investigator.
	Chemistry	X		X		X		May be drawn up to 3 days before the planned assessment.
	Urinalysis					X		May be collected up to 3 days before the planned assessment.
	Urine pregnancy test					X		Day 1 of every other cycle. Only to be performed on women of childbearing potential.
	PK sampling	X	X	X		X	X	See PK Schedule for collection information.
	Stored sample for pharmacogenetics	X						Collect once. Sample can be collected at any time if not collected on Day 1 of Cycle 1.
	Exploratory blood sample for biomarkers						X	Only to be collected on the same day when the CT scan is obtained (every 3 cycles starting with Cycle 3).
	Plasma biomarker sample	X				X		Collect prior to dosing on Day 1 of Cycles 1 and 3 only.
	ECG	X		X		X		Single local ECG collected at each time point. Day 1: predose, 10 min after EOI (±5 min), 30 min after EOI (±10 min), and >1 hour after EOI. Cycle 2-X: predose. However, if QTcF >480 msec is observed on Day 1, then 10 min after EOI (±5 min), 30 min after EOI (±10 min), and >1 hour after EOI should also be collected in subsequent cycles.
Optional Tumor Biopsy			X				Can occur at any time during patient's treatment.	

Study Period		Study Treatment Period						
		1		2		3-n ^a		
Cycle/Visit		14 days		14 days		14 days		
Duration		14 days		14 days		14 days		
Relative Day within Dosing Cycle		1	8	1	8	1	8	
Tumor Assessment	Radiologic imaging according to RECIST 1.1						X	For the first 52 weeks following enrollment, perform approximately every 6 weeks starting at the end of Cycle 3 (eg, Days 8-14). Thereafter, perform approximately every 12 weeks. The scanning interval (6 or 12 weeks [± 1 week]) should be maintained even if cycles are delayed. As a result, after Cycle 3, the scans may not always occur at the end of a cycle. The same method of imaging used at baseline should be used for each subsequent assessment. Scans should also be obtained as clinically indicated.
Tumor Assessment	Tumor measurement (palpable or visible)						X	Perform at least every 6 weeks starting in Cycle 3 on the same day as the radiologic imaging.
Adverse Events Collection/ CTCAE Grading		X		X		X		
Concomitant Medication Notation		X		X		X		
Lung Cancer Symptom Scale		X		X		X		The LCSS is to be administered prior to extensive interaction with site personnel and prior to administration of study drug.
Study Treatment	LY2606368	X		X		X		IV over approximately 60 (+10) min

Abbreviations: BSA = body surface area; CT = computed tomography; CTCAE = Common Terminology Criteria for Adverse Events (NCI 2009); ECG = electrocardiogram; ECOG = Eastern Cooperative Oncology Group (Oken et al. 1982); EOI = end of infusion; IV = intravenous; min = minute; LCSS = Lung Cancer Symptom Scale; PK = pharmacokinetic; QTcF = QT interval using Fridericia’s correction; RECIST 1.1 = Response Criteria In Solid Tumors Version 1.1 (Eisenhauer et al. 2009).

Table JTJH.2.3. Post-Treatment Follow-Up Schedule of Activities

Study Period		Post-discontinuation Follow-Up		
		Short-term Follow-Up	Long-term Follow-Up	
Duration		30 ± 5 days	60 ± 14 days	
Visit		801	802-X	
Relative day within a cycle		Period begins the day after stopping of study treatment and lasts approximately 30 days	Period begins 1 day after short-term follow-up period is completed and continues until death, study withdrawal, or the patient is lost to follow-up	
Procedure Category	Procedure			Comments
Physical Examination	Physical examination (including weight)	X		
	Vital signs	X		Includes blood pressure, pulse, and temperature.
	ECOG performance status	X		
Tumor Assessment	Radiologic imaging according to RECIST 1.1	X		The same method of imaging (CT scan, spiral CT, etc.) used at baseline should be used for each subsequent assessment. Not required if progressive disease is documented while on treatment or if there are clear signs of clinical progression.
	Tumor measurement (palpable or visible)	X		Performed at the same time as radiologic imaging.
Adverse Events Collection/CTCAE Grading		X	X	After Visit 801, only study treatment-related serious events are reported.
Concomitant Medication Notation		X		
Lab/Diagnostic Tests	Hematology	X		
	Chemistry	X		
	ECG	X		
	Exploratory blood sample for biomarkers	X		
	Plasma biomarker sample	X		
	Optional posttreatment biopsy		X	
Health Outcome Measure	Lung Cancer Symptom Scale	X		The LCSS will need to be administered prior to extensive interaction with site personnel.
Follow-Up	Survival Assessment		X	Approximately every 60 (±14) days (telephone assessment is acceptable).

Abbreviations: CT = computed tomography; CTCAE = Common Terminology Criteria for Adverse Events (NCI 2009); ECOG = Eastern Cooperative Oncology Group (Oken et al. 1982); LCSS = Lung Cancer Symptom Scale; RECIST 1.1 = Response Criteria In Solid Tumors Version 1.1 (Eisenhauer et al. 2009).

Table JTJH.2.4. Continued Access Schedule of Activities

	Study Treatment	Follow-Up ^a	
Visit	501-5XX	901	
Procedure ^b			Comments
AE collection	X	X	
Administer LY2606368	X		IV over approximately 60 (+10) minutes once every 14 days.

Abbreviations: AE = adverse event; IV = intravenously.

- a Continued access follow-up begins 1 day after the patient and the investigator agree that the patient will no longer continue treatment in the continued access period and lasts approximately 30 days. No follow-up procedures will be performed for a patient who withdraws informed consent unless he or she has explicitly provided permission and consent.
- b Efficacy assessments will be done at the investigator's discretion based on the standard of care.

3. Introduction

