6.1. Inclusion Criteria

Patients are eligible to be included in the study only if they meet all of the following criteria:

- [1] have histological or cytological diagnosis of ED-SCLC (Edge et al. 2010) and have received a prior platinum-based regimen
- Cohort 1: had an objective response to prior platinum-based therapy with subsequent progression ≥ 90 days after the last dose of platinum
 - Cohort 2: either did not have an objective response to prior platinum based therapy or had progression < 90 days after the last dose of platinum

If a patient has had more than one line of platinum therapy, the platinum sensitivity should be determined from the last exposure to platinum.

- [2] have a performance status of 0 to 1 on the Eastern Cooperative Oncology Group scale (Oken et al. 1982)
- [3] have discontinued all previous treatments for cancer and recovered from the acute effects of therapy. Patients must have discontinued from previous treatments, as shown below:

Previous Treatment	Length of Time Prior to First Dose of LY2606368
Cytotoxic therapies or targeted agents that are small molecule inhibitors	≥ 14 days
Biologic agents	≥ 14 days
Immunotherapy	≥ 14 days
Radiotherapy	≥ 14 days
Major surgery, excluding biopsy	≥ 14 days

- [4] have at least 1 measurable lesion using standard techniques by Response Evaluation Criteria In Solid Tumors (RECIST) 1.1 (Eisenhauer et al. 2009)
- [5] have given written informed consent/assent prior to any study-specific procedures
- [6] are of an acceptable age to provide informed consent according to the local regulations and are at least 18 years of age

[7] have adequate organ function, as defined below:

System	Laboratory Value
Hematologic	
ANC	$\geq 1.5 \times 10^9/L$
Platelets	$\geq 100 \times 10^9/L$
Hemoglobin	≥ 8 g/dL or ≥ 5 mmol
	Transfusions to increase the patient's hemoglobin level to meet enrollment criteria are not allowed in the 14 days preceding the first dose of study drug.
Hepatic	
Direct bilirubin	$\leq 1.5 \times ULN$
ALT and AST	$\leq 2.5 \times ULN$ OR $\leq 5 \times ULN$ if the liver has tumor involvement
Renal	
Serum creatinine OR Measured creatinine clearance OR Calculated creatinine clearance (using the CKP-EPI equation - see Appendix 6)	$< 1.5 \times ULN$ OR ≥ 50 mL/min/1.73 m ²

Abbreviations: ALT = alanine aminotransferase; ANC = absolute neutrophil count; AST = aspartate aminotransferase; CKP-EPI = Chronic Kidney Disease Epidemiology Collaboration; ULN = upper limit of normal.

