6.2. Exclusion Criteria

Patients will be excluded from the study if they meet **any** of the following criteria:

- [10] have received more than 2 prior therapies for ED-SCLC (including immunotherapy, targeted therapies, or chemotherapy)

Each line of therapy is preceded by disease progression. Discontinuation of a regimen without progression (for example, due to toxicity) or a switch of an agent within the same drug class (for example, cisplatin to carboplatin) within a regimen to manage toxicity does not define the start of a new line of therapy. Similarly, maintenance therapy (continuation maintenance or switch maintenance) will not be considered a new line of treatment.

- [11] have symptomatic central nervous system (CNS) malignancy or metastasis. Asymptomatic patients with treated CNS metastases are eligible for this study if they are not currently receiving corticosteroids to treat CNS metastases. CNS metastases should be stable for at least 14 days by clinical assessment, and patients should not have received corticosteroids to treat CNS metastases within 14 days of the first dose of study drug.
- [12] have a second primary malignancy that in the judgment of the investigator and Lilly may affect the interpretation of results
- [13] are currently enrolled in a clinical trial involving an investigational product or any other type of medical research judged not to be scientifically or medically compatible with this study
- [14] have previously completed or withdrawn from this study or any other study investigating LY2606368 or a CHK1 inhibitor or have shown hypersensitivity to any of the components of the LY2606368 formulation
- [15] have a known serious concomitant systemic disorder (for example, active infection or cardiac disease) that, in the opinion of the investigator, would compromise the patient's ability to adhere to the protocol
- [16] have a symptomatic human immunodeficiency virus (HIV) infection or symptomatic activated/reactivated hepatitis A, B, or C (screening is not required). If the medical history, symptoms, and/or laboratory values suggest that the patient may have HIV or hepatitis A, B, or C, appropriate assessment should be conducted to determine whether the patient should be excluded.
- [17] have a serious cardiac condition, such as:
- symptomatic congestive heart failure
 - New York Heart Association Class III/IV heart disease
 - unstable angina pectoris
 - symptomatic or poorly controlled cardiac arrhythmia

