7.7. Concomitant Therapy

No other chemotherapy, immunotherapy, cancer-related hormone therapy, herbal drugs intended to treat cancer, or experimental drugs will be permitted while the patients are on this study. Radiotherapy (including palliative radiotherapy) will only be permitted if it is agreed upon by the both investigator and Lilly. If the lesion that is to be treated is a target lesion, the lesion will be censored at the time of treatment. However, the patient may be eligible to remain on study drug treatment provided there are other lesions that can be followed for progression. Treatment delays of LY2606368 may be required if radiotherapy is administered. In addition, any disease progression requiring other forms of specific antitumor therapy will also necessitate early discontinuation from the study. Replacement hormonal therapy initiated before study entry will be allowed.

Patients should receive full supportive care during the trial. American Society of Clinical Oncology (ASCO) guidelines (Smith et al. 2015) should be followed for patients requiring support with granulocyte-colony stimulating factor (G-CSF). Primary or secondary prophylactic G-CSF support is permitted at the discretion of the investigator. Per the National Comprehensive Cancer Network (NCCN) guidelines, Phase 2 data support the use of pegfilgrastim in regimens with a 2-week cycle, and there is uniform consensus that this is appropriate (Category 2A) (NCCN guidelines for myeloid growth factors [WWW]). As a result, filgrastim, filgrastim biosimilars, or pegfilgrastim may be used.

Prophylactic antibiotics should be considered for use in patients that have experienced neutropenic fever or patients deemed at higher risk for neutropenic fever by the investigators. The treatment should be consistent with ASCO guidelines (Flowers et al. 2013).

Transfusion of packed red blood cells (RBCs) within 14 days of study entry is not permitted. The initiation of erythropoietin therapy to meet eligibility criteria is not permitted. Patients who are stable on erythropoietin for >1 month before study entry may continue their treatment. Erythropoietin and packed RBC transfusion may be used according to ASCO guidelines (Rizzo et al. 2008) if clinically indicated at any time during the study.

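### The baseline scan need not follow the last prior anticancer treatment, so shrinkage from treatment given between day -28 and day -14 can count towards ORR, mainly in Cohort 2

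*Protocol*

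**What the plan says.** **Baseline scan.** The imaging comment in Protocol Table JTJH.2.1 allows scans from routine care to serve as baseline "provided that they were done no more than 28 days before the first dose of study drug". Column positions in the extracted table cannot be relied on, but this comment is explicit.

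**Washout.** Inclusion [3] (Protocol 6.1) requires that patients "have discontinued all previous treatments for cancer and recovered from the acute effects of therapy". Its table is headed "Length of Time Prior to First Dose of LY2606368" and sets at least 14 days for cytotoxic and small-molecule agents, biologics, immunotherapy, radiotherapy and major surgery.

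**Measurable disease.** Inclusion [4] asks that patients "have at least 1 measurable lesion using standard techniques by Response Evaluation Criteria In Solid Tumors (RECIST) 1.1", with no date relative to earlier treatment.

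**Platinum timing.** Cohort 1 patients must have "had an objective response to prior platinum-based therapy with subsequent progression ≥ 90 days after the last dose of platinum". Cohort 2 patients "either did not have an objective response to prior platinum based therapy or had progression < 90 days after the last dose of platinum"; the first limb of that definition carries no date.

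**Radiotherapy on study.** Protocol 7.7: "If the lesion that is to be treated is a target lesion, the lesion will be censored at the time of treatment".

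**Analysis.** SAP Table JTJH.5.1 takes as baseline the last measure on or before first dose. SAP 5.10.1 derives best response from investigator assessment, counted from the start of study treatment, with every enrolled patient in the denominator and confirmation more than 4 weeks later.

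**The concern.** Both time limits are anchored to first dose and neither to the other. That leaves a stretch in which a patient can be irradiated or given a last dose of an earlier regimen after the scan against which response will be measured. Shrinkage from that treatment would be read at the end-of-Cycle-3 scan as shrinkage on LY2606368.

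The primary endpoint is a response rate without a concurrent control, so the two sources cannot be separated afterwards. The success counts are low (16 of 58 and 6 of 58), so a small number of such responses would matter. Protocol 7.7 shows that the sponsor recognises the problem for a target lesion irradiated during the study; its wording does not clearly reach the interval between baseline scan and first dose.

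**Working it through.** **1. The window.** Scan limit 28 days, washout 14 days: 28 - 14 = 14 days (day -28 to day -14) in which treatment can follow the baseline scan with every criterion met. The first post-baseline scan falls in days 8-14 of Cycle 3, about study days 36-42, so up to about 28 + 42 = 70 days can separate baseline from first assessment.

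**2. Does another rule close it?**
- Inclusion [4] has no date.
- The SAP baseline is the latest pre-dose measure. A later scan would replace the old one, but none is required.
- The per-protocol guideline in SAP 5.1 removes eligibility violations and significant deviations in efficacy assessment. This patient has neither.
- No planned sensitivity analysis addresses the case.

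**3. Which cohort?** In Cohort 1, progression must come at least 90 days after the last platinum dose, so that dose cannot fall in the window. Radiotherapy or a later non-platinum line can. Cohort 2 has no such protection and has the lower success count.

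**4. The plan's own figures.** Inputs from Protocol 10.1 and 10.3.4: n = 58 per cohort, look at 29; Cohort 1 floor 20%, target 35%, stop at 4 or fewer, success at 16 or more; Cohort 2 floor 5%, target 15%, stop at 0, success at 6 or more.

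Single look: P(Bin(58, p) >= r). Two-stage: the sum, over first-stage counts x that pass futility, of P(X1 = x) × P(X2 >= r - x), with 29 patients in each stage.

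| | Type I, single look | Power, single look | Type I, two-stage | Power, two-stage |
|---|---|---|---|---|
| Cohort 1 | 0.103 | 0.909 | 0.102 | 0.906 |
| Cohort 2 | 0.069 | 0.885 | 0.068 | 0.883 |

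Both powers agree with the stated approximately 90% to within 2 points.

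**5. Illustration of carry-over.** Let k of the 58 patients be confirmed responders only because of earlier treatment, with the drug at its floor rate p0 in the rest. Interim ignored, the chance of success is P(Bin(58 - k, p0) >= r - k).

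| k | Cohort 1: P(Bin(58 - k, 0.20) >= 16 - k) | Cohort 2: P(Bin(58 - k, 0.05) >= 6 - k) |
|---|---|---|
| 0 | 0.103 | 0.069 |
| 1 | 0.152 | 0.155 |
| 2 | 0.217 | 0.307 |

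With the futility look included and the k patients split at random between stages, k = 1 and 2 give 0.151 and 0.215 (Cohort 1) and 0.154 and 0.304 (Cohort 2). The interim barely changes the result.

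**6. From responders to exposed patients.** k counts confirmed responders, not patients treated in the window. If c is the chance, averaged over the whole cohort, that a patient who would not respond to the drug is scored a responder through carry-over, the effective rate is p0 + (1 - p0)c. Suppose 10% of Cohort 2 is exposed and 10% of those become carry-over responders (both assumptions). Then c = 0.10 × 0.10 = 1%, the effective rate is 0.05 + 0.95 × 0.01 = 0.0595, and the two-stage false-positive rate is 0.129 instead of 0.068. With c = 2% it is 0.208. The Cohort 1 figures are 0.133 and 0.169.

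**The case against.** The gap itself is hard to dispute; its likely size is open to challenge.

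- **Exposure has to exceed k.** Protocol 3.1 puts second-line response at 10% or less in refractory disease and about 20-25% in sensitive disease. At those rates, one or two carry-over responders need at least about 10 or 20 exposed patients in Cohort 2 (1/0.10 and 2/0.10), and 4-5 or 8-10 in Cohort 1. These rates describe a new line of treatment, not the last dose of a failing one, and the documents give none for radiotherapy. This stands, and it makes the table in step 5 an illustration, not a forecast.
- **Confirmation is demanding.** With scans about 6 weeks apart, shrinkage would usually have to last to about week 12, at least 14 weeks after the last prior treatment (2 + 12), in a tumor that the protocol calls rapidly growing. Tumor size is also a sum over target lesions, so irradiating one mass need not produce a partial response. This stands as a reduction of the risk.
- **Bias runs both ways.** With no treatment after the scan, growth before dosing counts against the drug. True, but that affects different patients and cannot be relied on to cancel carry-over.
- **Other rules may help.** Protocol 7.7 restricts other anticancer treatment on study, which could be read as applying from consent. That reading is not explicit, and routine-care scans and treatment before consent are the cases at issue. Response is also assessed under RECIST 1.1, which is not reproduced here, so one cannot assert that no rule on irradiated lesions exists there.

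A reader might also infer that the 28-day and 14-day limits contradict each other. They do not: both count back from first dose and can be met together. What is missing is an order between scan and treatment.

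**Conclusion.** The concern holds as a gap in how the primary endpoint is measured. A patient who meets every criterion can be treated after the baseline scan, and nothing in the protocol or SAP text keeps that treatment's effect out of ORR. The exposure is mainly in Cohort 2; in Cohort 1 it is confined to radiotherapy or a later non-platinum line.

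A reader might infer that ORR will be inflated, or that a positive result would be unreliable. The documents do not support that: they give no number of exposed patients, confirmation filters out short-lived shrinkage, and an old scan without later treatment pulls the other way. What they support is conditional. If one patient per cohort were a confirmed responder through carry-over alone, the false-positive chance at the floor would exceed the planned one-sided 0.10 in both cohorts (about 15% and 16%). Two would give 22% and 31%. The correction is worth making because it is cheap and protects an uncontrolled endpoint with low success counts.

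**What to change.** 1. **Table JTJH.2.1, imaging comment.** Allow a routine-care scan as baseline only if it was done within 28 days before first dose and after both the last dose of prior systemic anticancer therapy and the completion of any radiotherapy. Leave the washout in inclusion [3] unchanged.
2. **SAP 5.10.1.** Keep the primary analysis as it is. Add a conservative ORR sensitivity analysis that counts as non-responders those patients whose baseline scan predates their last prior anticancer treatment, and report their number by cohort.

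With the first change the 14-day window closes for every patient enrolled under it, and the false-positive rates return to the design values of 0.102 and 0.068. The second covers patients already enrolled and shows whether the issue arose at all.

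Cost: one sentence in the schedule and one analysis, using scan dates and the last-treatment dates needed to verify eligibility. A few patients would need a baseline scan repeated within the screening window. The sensitivity analysis may discard some genuine responses, so it should be read as a lower bound with respect to this problem and not as a replacement for the primary result.
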